9.2.1 Treatment Assignment Procedures

Patients will be assigned to screening using stratified block randomization. [name], who is not involved in subject testing or interventions will generate a computerized block randomization scheme to assign study identification numbers to either 5-Cog or control arms. Patients will be stratified by gender and age (< or >75 years). Briefly, an encrypted file containing the group assignment is prepared for each study identification number. The file is stored in RedCap the database program used for this trial. The assignments are presented to the research assistants (RA) in sequential order at the time the participant is enrolled, following the eligibility assessment, and

administer the indicated screen. Participants and the RA who administers the tests are not blinded to group assignment. However, investigators, data analysts collecting outcome data, and the statistician remain blinded to individual assignments.

9.3 Interim analyses and Stopping Rules

Due to the non-invasive nature of the protocol, it is not expected that early termination will be required due to adverse events. However, constant monitoring of the participants by [name], other investigators, and research staff will be maintained to ensure that AEs are not occurring. Early study termination will occur in the event of any unanticipated serious adverse event determined to be possibly, probably or definitely related to study procedures.

9.4 Outcomes

9.4.1 Primary outcome

Our primary outcome is **improved dementia care**. This outcome is collected prospectively from EMR and related medical records by data analysts (Administrative & Statistics Cores) and do not require patient interviews. This primary outcome is defined as meeting any one of the following endpoints within 90 days of the clinic visit at which the patient was randomized. Similar composite endpoints to define dementia care have been used in several prior clinical trials in cognitively impaired patients.³²⁻³⁶

1. New diagnosis of dementia (relevant ICD-10 codes) or MCI (331.83) documented in the EMR. The recent DSM-V criteria³⁷ include categories of ‘major neurocognitive disorder’ and ‘mild neurocognitive disorder,’ which overlap with dementia and MCI. These categories will also be included but a recent internal audit indicated that they are as yet not in widespread use in our primary care clinics (cf. specialty clinics).
2. Tests ordered for reversible causes of cognitive impairment as recommended by the published guidelines of professional societies (e.g. thyroid function tests, B-12 level, CT or MRI scans).^{15, 38-41}
3. New prescriptions for dementia medications in EMR.
4. Referral for cognitive/dementia evaluation by specialists (Neurology, Geriatrics or Psychiatry) in EMR.

9.4.2 Secondary outcomes

Health care utilization (emergency room visits and hospitalizations) for patients in both arms will be tracked up to 12 months from the clinic visit at which the patient was randomized and reviewed at regular intervals by data analysts throughout the study period. The data analysts will have no participant contact and be blinded to study assignment. The EMR system is in place in our institution. All visit notes and diagnoses are to be entered within 48 hours of the encounter.

9.5 Data Analyses

We will examine data for potential outliers and analyze the robustness of our findings

against them. We will perform per-protocol analysis to assess the sensitivity of our findings to protocol deviations. Furthermore, the impact of baseline imbalance will be determined by comparing the analysis outcomes with and without controlling for baseline attributes. Chi-square test will be used to compare ‘improved dementia care’ outcome within 90 days post-intervention between the intervention and control groups. Logistic regression model adjusted for covariates will also be used. We will use **intention to treat analysis**.⁵⁷ Pre-specified baseline covariates to account for **confounders** in the planned analysis include age, gender, education, and chronic illnesses. Baseline distribution of covariates will be compared to assess adequacy of randomization. We do not discount residual/unmeasured confounding – though this is more of an issue in observational studies without randomization. We will report adjusted and crude estimates of associations to assess confounding, and discuss limitations of the study.

Primary outcome: Chi-square test will be used to compare ‘improved dementia care’ outcome within 90 days post-intervention between the intervention and control groups. Logistic model adjusted for covariates will also be used.

Heterogeneity of treatment effect (HTE) is the nonrandom, explainable variability in the direction and magnitude of treatment effects for individuals within a population. The main goals of HTE analysis are to estimate treatment effects in clinically relevant subgroups and to predict whether an individual might benefit from a treatment. In this RCT, we will specifically address HTE due to gender (male/female), ethnicity (African-American/Hispanic/Caucasian) and education (less than high school/ high school graduate). Treatment effects in these subgroups will be evaluated using stratified analysis. Alternative, an interaction term between the subgroup characteristic and treatment group will also be tested.

Secondary outcome: Utilization is defined in terms of specialty visits, emergency room visits, and hospitalizations up to 12 months following the screening visit. This will be tracked via the EMR in both groups. The rates of utilization will be compared between the two groups using analytical approaches described for the primary outcome. We will also compare ‘days free of utilization’ (number of days from screening to first episode of health care utilization over follow-up) in both groups using linear mixed effect and survival models.^{58, 59}

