4 SELECTION AND ENROLLMENT OF PARTICIPANTS

Our target population is seniors with cognitive concerns in primary care clinics. While we anticipate that many potential participants might be attending Medicare Annual Wellness visit, we will also recruit eligible patients who will be attending the primary care clinic for other medical reasons.

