4.3 Study Enrollment Procedures

Potential participants may be referred by the clinic staff to the non-clinician research assistant (RA) by a message sent in the EMR, a phone call to the RA or by approaching the RA in person. Once a referral is received the RA will review the patient's electronic medical records or medical chart to determine their eligibility for participation based on the criteria above. Next, they will locate the patient within the clinic by asking the clinic staff to identify the patient.

Potential participants may also be identified by reviewing the daily clinic schedule on the electronic clinic schedule calendar. The RA will review all patients' charts that are ≥ 65 years and older with an appointment at the clinic that day to determine their eligibility based on the criteria described above. Next, they will locate the patient within the clinic by asking the clinic staff to identify the patient.

After identifying the patient referred by a clinic staff member the RA will confirm the cognitive complaint. Before offering a patient enrollment in the study, the RA will ensure that they (or their family member or friend, or a clinic staff member) have a cognitive complaint or concern about them. This information will be recorded in the database.

If the potential participant was identified by the RA from the daily schedule and determined to be eligible based on criteria from the EMR, the RA will greet the patient and say "I am X, and I am a RA. We are conducting a research study here at the clinic." The RA will give a study flyer to the potential participant and say, "Would you mind please reviewing this flyer and answering the questions on it? I will give you a few minutes, and will come back to review it with you. Do you have any questions, or problems reviewing

Flyer Questions:
 "Are you concerned about your memory?"

Yes No

"Are your loved ones concerned about your memory?"

Yes No

this flyer?” If the patient is there with family or friends, the RA can encourage the patient to let their family or friend review it with them if they are comfortable.

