5.2 Handling of Study Interventions

The tester will obtain informed consent, prior to randomizing patients to either the 5-Cog or control interventions. We will follow the example of other pragmatic clinical trials of dementia screening in primary care clinics⁵³ by randomizing at the patient level rather than at the level of providers or clinics. This will minimize effects of unmeasured case mix differences and clinic-level clustering. As noted by Fowler et al,⁵³ the risk for "spillover" from having participating primary care clinics treat both intervention and usual-care patients is likely to be small given low levels of dementia detection.⁵⁴ The patient-based randomization should conservatively bias results in favor of usual care. [name] (Statistics Core) will computer-generate a randomized block design which will be used to assign study identification numbers and place patients into either 5-Cog or control groups.

The IRB requires us to disclose the tests to participants in both study arms; therefore, it is not feasible to blind patients. Participants and the RA who carries out the 5-Cog or health literacy and grip strength assessments are not blinded to group assignment. However, investigators, data analysts collecting outcome data of improved dementia care, and the statistician remain blinded to individual assignments.

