9.2 Sample Size and Randomization

This randomized study has 600 subjects for each of the 2 groups. Assuming a non-completion rate of EMR entries of 10% over 90 days and that 25%, 30% or 35% of control subjects will experience ‘improved dementia care,’ we can detect odds ratios of 1.46, 1.43 or 1.42, respectively, on the effect of 5-Cog on improving dementia care with 80% power using a two-sided test with significance level of 0.05. There is a paucity of studies examining efficacy of brief cognitive screens in primary care. One non-randomized trial of

screening by medical assistants coupled with a decision tree in primary care clinics showed new physician action in 17% of patients with a positive screen in intervention sites compared to 1% in control sites.³⁶ Action included new dementia diagnosis, referral to specialist or initiating dementia treatment (similar to our primary outcome). While our projected effect size used for sample size estimation is conservatively lower than that reported in this previous study,³⁶ the effect size from this previous study was not used to calculate power given its preliminary, non-randomized nature but is presented in support of our assumptions. A review of 8 studies of detection of mild dementia in primary care showed that sensitivity ranged from 9% to 41%.⁵⁵ Detection rates in clinics are even lower for earlier dementia stages such as MCI.⁵⁶ These observations support our assumptions of lower rates of improved dementia care in our control group.

Cohort retention: This is not a major issue for this RCT as primary outcomes are based on clinical encounters information collected from EMR and other administrative data sources in patients residing in Bronx County and receiving primary care in our institution. Also, primary outcomes do not require repeat in-person testing after baseline assessments.

- *Non-completion:* We realize that not all patients will complete the additional tests described above as covariates or exploratory outcomes. We will complete as many of the tests as possible depending on patients' availability. Nonetheless, our overall sample size of 1,200 participants provides a sufficient pool to conduct sensitivity analyses assuming non-completion rate of 50%.

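### The adjusted logistic model in 9.5 omits visit type and treating physician; the comparison stays valid, but a modest amount of power in that supporting model is given up

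*Combined protocol and SAP*

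**What the plan says.** Section 9.5 tests the primary outcome with a chi-square test and adds a covariate-adjusted logistic model. The pre-specified covariates "in the planned analysis include age, gender, education, and chronic illnesses". Heterogeneity is to be examined by gender, ethnicity and education. The same section reports crude and adjusted estimates side by side as a way of judging confounding. Section 9.2.1 stratifies randomization by gender and age.

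All four outcome components in 9.4.1 are clinician actions found in the EMR within 90 days, and 5.1 sends the screening result to the treating physician. Section 4 says "While we anticipate that many potential participants might be attending Medicare Annual Wellness visit", then adds that eligible patients attending for other medical reasons will be recruited too. A primary care appointment that day is an inclusion criterion (4.1), and one route to candidates is "reviewing the daily clinic schedule on the electronic clinic schedule calendar" (4.3).

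The only text that bears on grouping is the case for randomizing individual patients in 5.2, repeated in 6.2.2: "This will minimize effects of unmeasured case mix differences and clinic-level clustering". Neither visit type nor physician is named as a covariate, stratum, subgroup or random effect.

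**The concern.** When the endpoint is physician behaviour, patient traits are an incomplete set of predictors. A wellness visit may carry a different background rate of cognitive work-up from a visit for another problem, and physicians may differ in how readily they order tests or refer. Randomizing patients balances these factors on average. It does not remove the outcome variance they create.

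What is at stake is efficiency in the supporting model. The design sits close to 80% power, so a few points have some value. There is also a risk in interpretation: adding strong predictors to a logistic model moves the odds ratio even under perfect balance, and 9.5 intends to read crude-to-adjusted differences as evidence on confounding.

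**Working it through.** **1. The plan's own figure.** Section 9.2 states "This randomized study has 600 subjects for each of the 2 groups". It continues "Assuming a non-completion rate of EMR entries of 10% over 90 days", which leaves n = 600 × 0.9 = 540 per arm, and supposes that "25%, 30% or 35% of control subjects will experience" the outcome. The stated detectable odds ratios are 1.46, 1.43 and 1.42, "with 80% power using a two-sided test with significance level of 0.05".

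Power = Φ{[√n(p1 − p0) − 1.96√(2p̄(1 − p̄))] / √(p0(1 − p0) + p1(1 − p1))}, with p1 = OR·p0/(1 − p0 + OR·p0) and p̄ the mean of p0 and p1.

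| Control rate | Stated OR | p1 | Power | OR at 80% power |
|---|---|---|---|---|
| 25% | 1.46 | 32.7% | 80.2% | 1.459 |
| 30% | 1.43 | 38.0% | 79.3% | 1.434 |
| 35% | 1.42 | 43.3% | 80.2% | 1.419 |

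The sample size reproduces. It has no term for visit type or physician.

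**2. Unadjusted reference.** Take 25% versus 32.7% (OR 1.458, log OR 0.3768). The variance of the log OR is 1/(540 × 0.25 × 0.75) + 1/(540 × 0.327 × 0.673) = 0.00988 + 0.00841 = 0.01829, so SE = 0.135. Then z = 0.3768/0.1352 = 2.786, and power = Φ(2.786 − 1.960) = 79.6%.

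**3. Visit type.** The documents give neither the wellness share nor its effect. Assume a 50:50 mix, control rates a and b averaging m = 25%, and one conditional log OR, β, chosen so that the intervention arm still averages 32.7%. Information in each visit type is 270·v0·v1/(v0 + v1), with v = p(1 − p); SE = 1/√(sum). The share of outcome variance explained is ((a − b)/2)²/[m(1 − m)].

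Worked case, 35/15: intervention rates are 44.6% and 20.9%, β = 0.400, information = 31.98 + 19.42 = 51.40, SE = 0.139, z = 2.870, power = 81.9%.

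| Control rates a/b | Visit-type OR | Variance explained | Conditional OR | SE | Power |
|---|---|---|---|---|---|
| none (unadjusted) | – | – | 1.46 | 0.135 | 79.6% |
| 30/20 | 1.7 | 1.3% | 1.47 | 0.136 | 80.1% |
| 35/15 | 3.1 | 5.3% | 1.49 | 0.139 | 81.9% |
| 40/10 | 6.0 | 12.0% | 1.55 | 0.146 | 84.9% |

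The gain is about 0.5, 2.3 and 5.3 points. The SE of the log OR goes up, not down. Power rises because the conditional OR moves further from 1 than the SE grows.

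**4. Physician.** The number of physicians and their variation are not given. Assume a normal physician intercept on the logit scale and the same marginal rates. Averaging the information in step 3 over that distribution gives an upper bound, because it treats physician effects as known. The last column is from simulation of the random-intercept logistic model with 15 or 30 physicians, unequal caseloads and 1,080 patients (all assumed).

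| Logit SD | Observed-scale ICC | Control rates, 10th–90th percentile physician | Upper bound on power | Simulated gain |
|---|---|---|---|---|
| 0 | 0 | 25% | 79.6% | none, and no loss |
| 0.5 | 0.044 | 14–37% | 81.4% | about 1 point |
| 0.7 | 0.081 | 11–42% | 82.9% | 2–3 points |
| 1.0 | 0.147 | 7–49% | 85.6% | about 5 points |

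**5. Validity of the unadjusted test.** In 20,000-run simulations (15–60 physicians, arms balanced within physician) with physicians differing only in baseline rate, type I error was 3.4–4.7% at latent-scale ICC 0.05–0.20. It is not inflated.

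**6. Arm-by-visit-type interaction.** The variance of the log ratio of ORs is the sum of 1/[n·p(1 − p)] over the four arm-by-visit cells. At 270 per cell and 25% versus 32.7% in both visit types it is 2 × (0.01975 + 0.01683) = 0.0732, so SE = 0.270. The ratio detectable with 80% power is exp(2.80 × 0.270) = 2.13. At 30% versus 38% it is 2.06. At a 30% wellness share the two figures are 2.29 and 2.20.

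**The case against.** The strongest reply is that nothing is broken. Patients are randomized individually, the primary test is a valid chi-square, and the sample size reproduces. The proposed change reaches only the supporting logistic model, so no gain passes to the primary test. The larger gains need large assumed heterogeneity: a visit-type OR of 6, or a control rate seven times as high at the 90th-percentile physician as at the 10th. The outcome also counts any qualifying EMR event in 90 days, not just those from the index visit or physician, which weakens both factors as predictors. Section 9.5 says covariates include the four named and promises analyses with and without baseline attributes, so the list might be read as open. Clinicians' own screener use is already tracked by arm (3 and 5.3.1). All of this stands as a limit on severity. It does not remove the point, because a covariate that is not named is not pre-specified.

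A reader might infer more than the documents support:

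- **That the omission biases the comparison or inflates type I error.** It does not (step 5). Only if physicians differed in their *response* to the result would the average effect be tested too liberally: rejection at zero average effect was about 5.1–11.4% in simulation (SD of log OR 0.2–0.4, latent ICC 0.05, both assumed). The documents say nothing about such variation, and a random intercept would not address it.
- **That adjustment is free.** It makes the OR conditional and raises its SE. Fixed stratification by physician, unlike a random intercept, lost about one point of power when physicians did not differ.
- **That the clinic schedule displays visit type and physician.** Section 4.3 says only that the schedule is reviewed and lists none of its fields. The EMR is the likelier source, but this too is an assumption.

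**Conclusion.** The omission is real and its cost is modest. Both covariate and subgroup lists in 9.5 hold only patient traits, while the endpoint is clinician action across two kinds of visit. Adding physician to the adjusted model would gain about 0 to 5 points of power; adding visit type would gain about 0.5 to 5. Both ranges rest on an assumed physician variance, wellness share and visit-type effect, with 540 per arm and 25% versus 32.7%. Moderate values give 1 to 3 points for each factor. The chi-square result, its validity and the sample size are untouched. Severity is low: a cheap improvement, not the correction of an error. An interaction with visit type is optional, since it could detect only a ratio of odds ratios of about 2 or more.

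**What to change.** In 9.5:

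- State that visit type (Annual Wellness or other) and treating physician for the index appointment are taken from the EMR before randomization and frozen at that value.
- Add visit type as a fixed effect and physician as a random intercept to the adjusted logistic model. Keep the chi-square test as it is.
- State that the adjusted OR is conditional and can differ from the crude OR without any confounding. Then either report a standardized (marginal) risk difference or OR beside it, or drop the reading of the crude-to-adjusted gap as a measure of confounding.
- If an arm-by-visit-type interaction is added, label it exploratory and give its detectable size.

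The cost is two extra EMR fields, a slightly more complex supporting model and a few lines of text. Sample size, randomization and clinic procedures do not change.

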3 STUDY DESIGN

We propose to conduct a single-blind RCT to validate the 5-Cog battery and decision tree (Fig. 1). The trial will span 42 months and involve an ethnically diverse Bronx primary care population of 1,200 older patients with cognitive concerns (Fig. 2). We chose an active control (health literacy and grip) to balance time and tester exposure in the 5-Cog group. Our primary outcome is improved dementia care, which is an outcome that informs health decisions and is valued by primary care clinicians, older patients and their caregivers. We bring together an inter-disciplinary team with major aging and clinical trial experience. We have developed partnerships with clinicians in our primary care clinic site.

[figure not shown]
Design considerations: We will take a pragmatic, real world approach in our trial. We will not ask physicians to deny patients any procedures offered routinely. For instance, clinicians have access to the PMIS and other cognitive screeners (not included in the 5-Cog screen) in our EMR. We will not ask clinicians to avoid using these screeners in enrolled patients. But we will track cognitive screener use by clinicians in control and 5-Cog arms via the EMR. We hypothesize that time constraints and other barriers as well as the absence of the MCR and Symbol Match procedure in the EMR will limit use and efficacy of cognitive screeners by primary care physicians. The proportion of older women is higher than men in our clinics and aging studies.^{3, 14, 31} Consistent with our pragmatic approach,

we will not strive for equal sex distribution within a study arm, but balance sex distribution by selecting gender as a stratification variable. There is no trial design without weakness and we will clearly state these in any publications.

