6.2.2 Randomization & Assessments

Randomization

The tester will obtain informed consent, prior to randomizing patients to either the 5-Cog or control interventions. We will follow the example of other pragmatic clinical trials of dementia screening in primary care clinics⁵³ by randomizing at the patient level rather than at the level of providers or clinics. This will minimize effects of unmeasured case mix differences and clinic-level clustering. As noted by Fowler et al,⁵³ the risk for "spillover" from having participating primary care clinics treat both intervention and usual-care patients is likely to be small given low levels of dementia detection.⁵⁴ The patient-based randomization should conservatively bias results in favor of usual care.

[name] (Statistics Core) will computer-generate a randomized block design which will be used to assign study identification numbers and place patients into either 5-Cog or control groups. Patients will be stratified by gender and age (< or >75 years). Briefly, an encrypted file containing the group assignment is prepared for each study identification number. The file is stored in RedCap the database program used for this trial. The assignments are presented to the RA in sequential order at the time the participant is enrolled, following the eligibility assessment, and administer the indicated screen. Participants and the RA who administers the tests are not blinded to group assignment. However, investigators, data analysts collecting outcome data, and the statistician remain blinded to individual assignments.

Assessments

Intervention arm (5-Cog): This simple, 5-minute procedure will identify older persons with cognitive impairment in primary care settings, and flag them for further evaluation. The 5-Cog battery includes the PMIS, MCR diagnosis,⁶⁻⁸ and the paper-based Symbol Match test. Our cognitive assessment algorithm will sort patients with or at high risk of developing ‘cognitive impairment’ from those with ‘no cognitive impairment’. Moreover, it is coupled with a decision tree to guide clinicians through the necessary steps to follow up on 5-Cog results. Because primary care clinicians and staff may not have the time to complete even a 5-minute screen,^{12, 15, 16} non-clinicians (RAs) will administer the 5-Cog and communicate the results to primary care physicians for further action.

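### Randomisation is stratified by gender and age, but the evident lead test of the primary outcome is a crude chi-square that uses neither factor

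*Combined protocol and SAP*

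**What the plan says.** Section 9.2.1 states: "Patients will be assigned to screening using stratified block randomization". Section 6.2.2 gives the factors: "Patients will be stratified by gender and age (< or >75 years". Section 3 explains the choice for gender, which is to "balance sex distribution by selecting gender as a stratification variable"; it gives no corresponding reason for age.

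Section 9.5 names the analyses of the primary outcome twice, in the same order each time. A chi-square test comes first and compares the composite "outcome within 90 days post-intervention between the intervention and control groups. Logistic model adjusted for covariates will also be used". The covariates "in the planned analysis include age, gender, education, and chronic illnesses", so both stratification factors are in the adjusted model. The form of age in that model is not stated. Adjustment is given two purposes. The effect of baseline imbalance is to be judged by "comparing the analysis outcomes with and without controlling for baseline attributes", and the plan adds: "We will report adjusted and crude estimates of associations to assess confounding".

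The Secondary outcome paragraph of 9.5 applies the same approaches to the utilization rates. For power, section 9.2 says "we can detect odds ratios of 1.46, 1.43 or 1.42, respectively" at control rates of 25%, 30% and 35%.

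**The concern.** When randomisation is balanced within strata and the strata predict the outcome, the difference between arms varies less than a crude test assumes. The crude test is then slightly conservative and gives up some power. Conditioning on the factors recovers that power. It costs almost nothing here, because gender and age must be known for every patient who is randomised, so no patient is lost.

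The second issue is which p-value decides the trial. The plan produces a crude and an adjusted result for one primary hypothesis and never formally ranks them. If they fall on opposite sides of 0.05, a reader has only word order to go by, and word order points to the less efficient test.

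**Working it through.** **1. Reproduce section 9.2.** The inputs are 600 per arm less 10% non-completion (540), control rates p0 of 25%, 30% and 35%, a two-sided 0.05 level and 80% power. No test is named.

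- Intervention rate: p1 = OR·p0 / (1 − p0 + OR·p0), giving 32.7%, 38.0% and 43.3%.
- Power = Φ{[(p1 − p0) − 1.96·√(2p̄(1 − p̄)/n)] / √[(p0(1 − p0) + p1(1 − p1))/n]}, where p̄ is the mean of the two rates.
- At a 30% control rate: p1 = 0.429/1.129 = 0.380 and p̄ = 0.340. The two standard errors are 0.02883 and 0.02873. Then (0.07998 − 0.05651)/0.02873 = 0.817, so power is 79.3%. At 25% and 35% it is 80.2%.
- Solving for 80% power gives odds ratios of 1.459, 1.434 and 1.419, against the stated 1.46, 1.43 and 1.42. With 600 per arm they would be 1.432, 1.409 and 1.394, which do not match.

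The planned power is therefore that of an unadjusted two-proportion comparison in 540 per arm.

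**2. Compare the tests by simulation.** There were 20,000 trials per scenario, at 30% versus 38% and under the null (30% in both arms), with 1,080 patients and permuted blocks of 4 within gender-by-age strata. The following are assumptions, because the documents do not give them:

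- 65% women and 40% in the older stratum.
- Log-odds (weak/moderate/strong) for age of 0.2/0.4/0.6 per SD and for sex of 0.1/0.2/0.3.
- Unmodelled education 0.1/0.25/0.4 and illness 0.2/0.4/0.6 per SD.

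Intercepts were set to keep the marginal rates fixed.

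| | Weak | Moderate | Strong |
|---|---|---|---|
| Power, crude chi-square (%) | 79.5 | 79.4 | 80.1 |
| Power, logistic, gender + two-level age (%) | 79.7 | 80.0 | 81.3 |
| Power, logistic, gender + age in years (%) | 79.8 | 80.3 | 82.0 |
| Gain, age in years (points) | 0.3 | 0.9 | 1.9 |
| Monte Carlo SE of gain (points) | 0.08 | 0.11 | 0.14 |
| Opposite sides of 0.05, age in years (%) | 1.3 | 2.6 | 3.7 |
| – model alone significant (%) | 0.8 | 1.7 | 2.8 |
| – chi-square alone significant (%) | 0.5 | 0.9 | 0.9 |
| Type I error, chi-square (%) | 5.1 | 4.6 | 4.6 |
| Type I error, model with age in years (%) | 5.2 | 4.8 | 5.2 |
| Mean odds ratio, crude | 1.43 | 1.43 | 1.43 |
| Mean odds ratio, adjusted | 1.44 | 1.45 | 1.47 |
| Risk difference, crude and standardised (points) | 8.0 | 8.0 | 8.0 |

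With two-level age the gain is 0.2/0.5/1.2 points, and disagreement at 0.05 is 0.2/0.5/1.2%.

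**3. Express the gain in patients.** Going from 540 to 545 per arm raises the crude test's power from 79.31% to 79.68%, or 0.037 points per patient. Then 0.30/0.037 ≈ 8 and 0.88/0.037 ≈ 24. The strong case, 1.92/0.037 ≈ 52, becomes about 54 once the flattening of the power curve is allowed for.

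**4. Other control rates (12,000 trials per scenario).** At 25% the gain is 0.3/0.9/1.8 points and disagreement 1.3/2.2/3.2%. At 35% they are 0.5/1.3/2.0 points and 1.3/2.4/3.3%.

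**5. Cross-check by another method.** A Mantel-Haenszel test stratified by gender and two-level age was compared with the chi-square in 40,000 trials per scenario (65% women and 50% in the older stratum, assumed). The chi-square lost about 0 to 3 points of power. At the extreme (age OR 4, gender OR 2, control rate 30%) power was 81.0% against 84.0%, and the chi-square's type I error had fallen to about 3.9%. The stratified test stayed between 4.8% and 5.1% throughout.

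**The case against.** The strongest case is that nothing here is broken. The chi-square holds its type I error and delivers the power planned in section 9.2. Age and gender are already pre-specified in the logistic model, and both results will be reported. Calling the chi-square the lead analysis is an inference, since no section ranks the two. The gain depends on assumed covariate strengths and is near nil at the weak end. Much of it comes from age in years, although the stratification factor was two-level age. And naming any one primary analysis would settle which p-value counts.

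Most of this is factually right and limits the point. It would be wrong to say that the plan ignores the factors altogether. The case for acting still stands:

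- The lead reading has support in the order of the tests, in the wording that makes the model an addition, and in the stated purpose of adjustment. Section 9.2 is consistent with it. If neither analysis leads, the need to choose one is greater.
- The 1–4% disagreement is the right figure for the model proposed here. The smaller two-level figures are shown beside it.
- Either test could be named primary. The adjusted model is the better choice because it respects the randomisation and is at least as powerful in every prognostic scenario examined.

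**Conclusion.** The concern holds as a recommended improvement, not as a validity failure. The evident lead test leaves out both stratification factors, and so gives up about 0.3 to 1.9 points of power at 30% versus 38% (0.2 to 1.2 if age enters as two levels). There is a 1–4% chance that it and the gender-and-age model disagree at 0.05. The size rests on assumed covariate strengths and an assumed sex and age mix. The direction was the same at all three control rates and by the second method whenever the factors were prognostic. The utilization rates inherit the same analysis.

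**What to change.** In section 9.5:

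- Make the primary analysis a logistic regression of the 90-day outcome on arm, gender and age in years, in all randomised patients with outcome data. Age in years also avoids the printed age strata, which place a patient aged exactly 75 in neither.
- Report the adjusted odds ratio with a model-standardised risk difference.
- Label the crude chi-square and crude odds ratio as sensitivity analyses.
- State that the same adjustment applies to the utilization rates.
- Keep the model with education and chronic illnesses as supportive. Use values obtained before the clinician visit and do not drop patients with a missing covariate. Section 3 describes collecting these data at recruitment, whereas 6.2.2 lists them among assessments done after that visit. The extent of missingness is not given.

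The cost is wording, settled before unblinding, with no new data. The one downside is that the adjusted odds ratio is conditional, averaging 1.44 to 1.47 where the crude one is 1.43, so it is not directly comparable with section 9.2. The standardised risk difference covers this. The 1,200 patients and the section 9.2 figures stay as they are.
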